### **Assessment of model assumptions**

- The trial was powered to detect an RRR of 1.25 with 90% power; this requires 843 sustained recoveries among the 1000 participants by Day 90. The rate of recoveries will be monitored, overall and within the two disease severity strata. Deviations of the observed distribution from the hypothesized distribution in the control arm will be monitored, and the impact on the power of the trial will be assessed. Prior to the completion of the trial for the investigational agent, sample size will be re-estimated by the blinded statisticians on the study team, based on the pooled rate of *sustained recovery*.

- The Fine-Gray model assumes that the sub-distribution rate ratio for *sustained recovery* is constant over time, similar to Cox proportional hazards models. The assumption of constant RRR will be tested by including an interaction effect between time and treatment indicator.

## Sensitivity Analyses

- As sensitivity analyses, the primary comparison will be repeated after excluding participants who did not receive any of the investigational agent/placebo (modified intention-to-treat).
- Sensitivity analyses for the primary endpoint comparisons will include consideration of home oxygen above pre-morbid oxygen use (described in section 4.2.2 item 12 of the protocol). For these sensitivity analyses, *sustained recovery* will be re-defined as:
  - “Discharged to home, alive at home without use of continuous supplemental oxygen for an uninterrupted 14 day period”
  - “Discharged to home, alive at home for an uninterrupted 14 day period, and no supplemental oxygen use at the end of the 14 day period”
- If the RRR is not constant (test described under “assessment of model assumptions” above), as a sensitivity analysis, the RRR will be estimated within time periods, for example, Day 14-28, Day 29-60, Day 61-90.
- Additional sensitivity analyses are described under “censoring” above.

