## 5 Baseline Characteristics

Baseline characteristics will be based on information collected on baseline and screening forms. For the open report, baseline characteristics will be summarized pooled across the two treatment groups (investigational agent and the “pooled” control group as described in section 2 above).

For the closed report, baseline characteristics will be summarized by treatment group.

The following baseline characteristics will be reported; unless noted otherwise, categorical variables will be summarized with numbers (%) in each category, and continuous variables will be summarized with median (IQR); in the open report, in addition, the mean (SD) and range may be provided. When enrolment has been completed, frequency distributions of these characteristics, including cut points for discretizing continuous measures, will be considered for defining subgroups in the final report.

- Demographics
  - Age: distribution in categories 18-29, 30-39, 40-49, 50-59, 60-69, 70-79,  $\geq 80$  years; and summary as continuous variable
  - Sex at birth: number (%) male, female
  - Ethnic group: number (%) Asian, Black, Latino/Hispanic, White, other
  - Type of residence (“home”)
  - Country of enrolment
- COVID-19 related characteristics
  - Duration of symptoms prior to enrolment
  - Use of remdesivir prior to enrolment
  - Pulmonary and pulmonary+ ordinal outcomes, number (%) in each category
  - NEWS: summary as continuous variable
  - Respiratory function scale (modified Borg dyspnea scale; continuous outcome)

- Disease severity randomization stratum (for investigational agents that enrol in both strata), number (%) in each category
- Receipt of SARS-CoV-2 vaccination, and type of vaccine (and if received as part of a blinded clinical trial, in which case the vaccine may be active or control)
- Other clinical characteristics
  - Concomitant treatments
  - Corticosteroid use will be summarized overall, and separately by oxygen requirement at baseline (no supplemental oxygen, < 4 L/min, conventional supplemental oxygen  $\geq$  4 L/min, high-flow oxygen or mechanical ventilation/ECMO)
  - History of chronic conditions (cardiovascular disease, diabetes, asthma, chronic obstructive pulmonary disease, hypertension, chronic kidney disease, hepatic impairment, cancer, or immunosuppressive disorder [HIV, and other than HIV])
  - Prior cerebrovascular event
  - Prior myocardial infarction (MI)
  - Requirement of continuous chronic supplemental oxygen

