### 8.1 Primary Efficacy Endpoint and Primary Analysis

The **primary efficacy outcome** of the trial is “time from randomization to *sustained recovery* through Day 90”. *Sustained recovery* is defined as being discharged from the index hospitalization, followed by being alive and *home* for 14 consecutive days.

**Comment:** The shortest possible time to sustained recovery is 14 days (this would require the patient to be discharged from the hospital on the day of randomization), and a patient would have to be discharged from the index hospitalization no later than Day 76 to achieve *sustained recovery* by Day 90.

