## Appendix A. Definition of the Pulmonary and Pulmonary+ ordered categorical outcomes

The Pulmonary categorical outcome is primarily defined based on oxygen requirements. The categories of the Pulmonary+ outcome are similar, except that categories 4 and 5 also capture selected extra-pulmonary complications, highlighted in red below.

Pulmonary outcome	Pulmonary+ outcome
1. Can independently undertake usual activities with minimal or no symptoms	1. Can independently undertake usual activities with minimal or no symptoms
2. Symptomatic and currently unable to independently undertake usual activities but no need of supplemental oxygen (or not above premorbid requirements)	2. Symptomatic and currently unable to independently undertake usual activities but no need of supplemental oxygen (or not above premorbid requirements)
3. Supplemental oxygen (<4 liters/min, or <4 liters/min above premorbid requirements)	3. Supplemental oxygen (<4 liters/min, or <4 liters/min above premorbid requirements)
4. Supplemental oxygen ( $\geq 4$ liters/min, or $\geq 4$ liters/min above premorbid requirements, but not high-flow oxygen)	4. Supplemental oxygen ( $\geq 4$ liters/min, or $\geq 4$ liters/min above premorbid requirements, but not high-flow oxygen) or any of the following: stroke (NIH Stroke Scale [NIHSS] <math>\leq 14</math>), meningitis, encephalitis, myelitis, myocardial infarction, myocarditis, pericarditis, new onset CHF NYHA class III or IV or worsening to class III or IV, arterial or deep venous thromboembolic events
5. Non-invasive ventilation or high-flow oxygen	5. Non-invasive ventilation or high-flow oxygen, or signs and symptoms of an acute stroke (NIHSS >14)
6. Invasive ventilation, extracorporeal membrane oxygenation (ECMO), mechanical circulatory support, or new receipt of renal replacement therapy	6. Invasive ventilation, ECMO, mechanical circulatory support, new receipt of renal replacement therapy, or vasopressor therapy
7. Death	7. Death

The term “usual activities”, in categories 1 and 2 for both outcomes, refers to activities of daily living that the participant was able to undertake prior to the current illness.

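### The home-oxygen sensitivity definitions of sustained recovery omit the pre-morbid qualifier stated in their own lead-in, so unchanged chronic oxygen use can count as non-recovery

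*SAP*

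**What the plan says.** The primary endpoint in SAP section 8.1 "is defined as being discharged from the index hospitalization, followed by being alive and *home* for 14 consecutive days". It sets no condition on oxygen.

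Under Sensitivity Analyses in the same section, the purpose of the oxygen analyses is stated first: "Sensitivity analyses for the primary endpoint comparisons will include consideration of home oxygen above pre-morbid oxygen use", with a pointer to its source, "described in section 4.2.2 item 12 of the protocol". Sustained recovery is then re-defined in two ways, each for a participant discharged to home:

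- Definition 1: "alive at home without use of continuous supplemental oxygen for an uninterrupted 14 day period".
- Definition 2: "alive at home for an uninterrupted 14 day period, and no supplemental oxygen use at the end of the 14 day period".

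Two other places bear on this. SAP section 5 lists "Requirement of continuous chronic supplemental oxygen" among the baseline characteristics, so such participants are expected. SAP Appendix A writes the pre-morbid reference point into categories 2 to 4 of both ordinal outcomes; category 2, for example, includes "no need of supplemental oxygen (or not above premorbid requirements".

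**The concern.** The lead-in and the definitions do not agree. The lead-in counts only oxygen beyond the pre-illness level. The definitions count all continuous oxygen (definition 1) or any oxygen at the end of the period (definition 2). Both are set out as complete endpoint definitions, so a programmer could reasonably code them as they stand.

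These analyses ask whether the treatment comparison survives when people sent home with new oxygen are not called recovered. If people whose oxygen use has not changed are also recoded, a departure from the primary result can no longer be attributed to COVID-19-related oxygen need. The conflict also leaves a coding choice open that should be settled before treatment comparisons are seen.

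**Working it through.** **Step 1. Apply each text to the possible cases.** Each participant is alive, discharged and at home for 14 consecutive days, and the oxygen use described continues.

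| Oxygen before illness | Oxygen at home afterwards | Primary endpoint | Purpose in lead-in | Definition 1, literal | Definition 2, literal |
|---|---|---|---|---|---|
| None | None | Recovered | Recovered | Recovered | Recovered |
| None | New, continuous | Recovered | Not recovered | Not recovered | Not recovered |
| Continuous | Same as before | Recovered | Recovered | Not recovered | Not recovered |
| Intermittent | Same as before | Recovered | Recovered | Recovered | Not recovered if in use at the end of the 14 days |

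The third row is the conflict: under both definitions it is coded exactly like the second row, which the lead-in means to separate from it. The fourth row shows that definition 2 reaches further than definition 1.

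**Step 2. Compare with the rest of the SAP.** Appendix A measures oxygen against the pre-morbid level. Section 8.1 likewise defines home by where the participant lived before admission. The two oxygen definitions are the exception.

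**Step 3. Reproduce the plan's event target, for scale only.** Inputs from SAP section 1.4: recovery rate ratio 1.25, one-sided level 0.025, power 90%, equal allocation.

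Events = 4 × (1.960 + 1.282)² / (ln 1.25)² = 844.1, which agrees with the stated 843 to within rounding.

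Power at *d* events = Φ(√(*d*/4) × ln 1.25 − 1.960). At *d* = 843 this is 0.900.

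**Step 4. Size under assumed shares.** The documents give no share of chronic oxygen users. Assume a share *p* of the 1,000 participants, recovering at the overall planned rate of 843/1000 = 84.3%, none of whom can meet the literal definition. Events recoded = 843 × *p*.

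| Assumed *p* | Events recoded | Events left | Nominal power at 1.25 |
|---|---|---|---|
| 0 | 0 | 843 | 0.900 |
| 1% | 8.4 | 834.6 | 0.897 |
| 2% | 16.9 | 826.1 | 0.894 |
| 3% | 25.3 | 817.7 | 0.891 |
| 5% | 42.2 | 800.8 | 0.884 |

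These figures describe the sensitivity analyses only.

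**The case against.** The best defence is that the qualifier already governs. The lead-in says which oxygen is meant, the definitions are introduced as serving those analyses, and the lead-in cites protocol section 4.2.2 item 12 as the source. The protocol text available for this review is the agent appendix H1, so item 12 could not be read and may state the rule in full. This stands as a limit on certainty about what will be coded. It does not remove the mismatch in the SAP, where two self-contained definitions lack the condition their introduction states.

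Three stronger readings are tempting, and the documents do not support them.

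- A reader might infer that nobody on chronic home oxygen can ever be counted as recovered. Definition 1 bars only continuous oxygen, so intermittent users can meet it, and definition 2 looks only at the end of the period. Failure on both counts is confined to those who remain on continuous chronic oxygen.
- A reader might infer that this undermines the main robustness check of the trial. Section 8.1 lists several sensitivity analyses, including modified intention-to-treat, period-specific rate ratios and the censoring analyses. No event target, monitoring boundary or futility rule uses the oxygen definitions.
- A reader might infer that an uneven split of chronic users would bias the comparison. A difference of 10 users between arms of 500 moves the recovery difference by at most 10/500 = 2.0 percentage points, or 0.843 × 2.0 = 1.7 points at the planned recovery rate. With 30 users in all (3%), a 20 to 10 split or worse has probability 2 × P(Bin(30, ½) ≥ 20), about 0.10. With 50 users, a 30 to 20 split or worse has probability about 0.20. With 10 users, a 10 to 0 split has probability 2/1024, about 0.002. This is ordinary sampling variation, which the test's type I error already covers. The same rule applies to both blinded arms, so it creates no systematic difference under the null.

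**Conclusion.** The point holds as a conflict between a stated purpose and the rules meant to carry it out. Followed literally, those rules would misclassify participants who return to unchanged continuous chronic oxygen, and definition 2 may also misclassify intermittent chronic users. What is lost is a clear interpretation of two pre-specified sensitivity analyses.

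The likely effect on events and power is small: about 8 to 42 of 843 recoveries, and nominal power of 0.897 to 0.884 against 0.900. That range rests on an assumed share of 1% to 5% and on chronic users recovering at the overall rate; neither figure is in the documents. The primary analysis does not change. Whether the misclassification would occur in practice depends on protocol section 4.2.2 item 12 and on how the lead-in is applied. It is worth correcting because the conflict is plain on the page and the correction is cheap.

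**What to change.** Before unblinding, reconcile both definitions with the lead-in and with protocol section 4.2.2 item 12, and state in each that only oxygen above pre-morbid use counts against recovery. At the least, apply this through the chronic-oxygen item in SAP section 5, so that participants with that requirement at baseline are not coded as non-recovered for unchanged chronic use. State also how intermittent chronic users are handled under definition 2, since the baseline item covers only continuous use.

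The cost is a few words in the SAP and a small change to the endpoint programming; this minimum version uses a variable already listed. The limit is that the baseline item records a requirement, with no flow rate stated, and the schedule in SAP Appendix D has no line that names home oxygen flow. If pre-morbid flow is not recorded, an increase over chronic use cannot be detected in these few participants, and the SAP should say so.

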## 8.2 Key Secondary Outcomes

- Mortality is a key secondary outcome; analyses are described in section 7.
- To supplement the separate analyses of time to sustained recovery and time to death, the two endpoints will be analyzed jointly using the “win ratio” method for the composite outcome of time to recovery or death. The win ratio will be calculated using the matched pairs method described in Pocock (2012). Pairs will be formed by ranking the participants in each treatment group according to a risk score, described in section 13.2, and pairing the participants in groups A (here referring to the investigational drug) and B (referring to control) with equal ranks. Details are given below.
  - If both treatment groups have the same number of observations, the win ratio is calculated as follows:
 

**Step 1:** Calculate the risk score for all participants, and order participants by the risk score in each treatment group. If needed, break ties at random. Each participant forms a “matched pair” with the participant of equal rank order in the other treatment group.

**Step 2:** For each pair, determine whether the participant in group A wins, loses, or neither:

    - a. *Compare pairs for time to death, for all pairs where one or both participants died.* If the participant in group A died, wins and losses are computed as follows:
      - If the matched participant in group B has longer follow-up, then A loses and B wins.
      - If the matched participant in group B has shorter follow-up and is alive at the censoring date, then neither group wins.

Repeat for pairs where the participant in group B died.

b. *Compare remaining pairs for time to sustained recovery.*

- If A achieved sustained recovery, and time to sustained recovery is longer for B, then A wins and B loses; vice versa for B.
- If A achieved sustained recovery, and B was censored without reaching sustained recovery before A reached sustained recovery, then neither group wins; vice versa for B.
- Otherwise, neither group wins.

**Step 3:** Calculate the win ratio as the number of wins in group A divided by the total number of pairs with a win or a loss in group A. Calculate the 95% CI for the win ratio and p-value as described in Pocock (2012).

- If one treatment group has more participants than the other, select  $|n_A - n_B|$  participants at random from the larger group and delete. Calculate the win ratio, 95% CI and p-value for the resulting matched pairs. Repeat the random selection of observations to delete 501 times; identify the matched pairs data set that corresponds to the median win ratio; the final values of the win ratio, 95% CI and p-value are those calculated from this data set.
- If both treatment groups have the same number of observations, but some ranked risk scores are tied within a treatment group, a similar process may be used to repeat the random breaking of ties, with the final win ratio chosen as the median over repeated random tie breaks.

With this approach, time to death is first used to determine the winning group (i.e., longer time to death), then time to sustained recovery is used to determine the winning group (i.e., shorter time to recovery): in this manner, the win ratio combines these conflicting outcomes into a composite while recognizing the importance of mortality.

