### **Sample size**

This phase III trial is planned to provide 90% power to detect a 25% increase in the rate of sustained recovery for an investigational agent compared to placebo at the 0.025, 1-sided level of significance. This requires 843 primary events (i.e., participants who achieve sustained recovery). Randomization of 1,000 participants, equally allocated to each investigational agent and placebo, followed for 90 days is estimated to result in the required number of primary events. The event target may be achieved earlier if more than 1,000 participants are enrolled. Sample size will be evaluated periodically by study team members who are blinded to interim results on treatment difference and may be increased to maintain power for the hypothesized difference in sustained recovery between the investigational agent and placebo.

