## 1.4 Sample Size Estimates

The planned sample size for each pairwise comparison is 1,000 participants (500 participants in each group). The sample size is sufficient to detect a recovery rate ratio (RRR) of 1.25 for time to sustained recovery with 90% power, using a one-sided test with a significance level of 0.025. The treatment groups are compared using Gray’s test with  $\rho=0$ , the competing risks analogue of the log-rank test.

Sample size calculations are described in detail in Section 6.3 of the protocol.

Blinded sample size re-estimation will be carried out before enrollment is complete to determine whether the planned sample size of 1,000 participants followed for 90 days will yield the planned number of 843 primary events. The blinded sample size re-estimation does not involve unblinding of the treatment difference. It will be based on the pooled outcome data. Sample size may be increased to achieve the event target in the planned follow-up of 90 days. A

sample size increase may also be considered in order to achieve the event target before all participants are followed for 90 days.

When 300 participants (150 per study arm) are enrolled and have Day 5 outcome data, an early futility assessment is planned. This assessment will be based on two ordinal outcomes, denoted as “pulmonary” and the “pulmonary+”; both are ordered categorical outcomes with 7 categories, assessed on Day 5 (the two outcomes are described in [Appendix A](#)). Treatment groups will be compared using proportional odds models. With 300 participants, the early futility assessment is powered to detect a summary OR=1.60 with power of 95%, using a one-sided test with significance level of 0.30. Given the two-outcome decision rules, an investigational agent with a summary OR=1.60 at Day 5 for both outcomes, would pass the futility assessment with a power between 93% and 98%, and a type I error between 0.21 and 0.39.

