### Censoring for time-to-event analyses

For **interim** analyses, the type of censoring used will depend on the data collection schedule.

- If the reporting of the endpoint is data-driven (e.g., SAEs and deaths are reported as they occur), then follow-up is censored at the administrative censoring date, at the date of withdrawal, or loss to follow-up, whichever occurs earliest.
- If the date of the event is elicited retrospectively at fixed study visits spaced more than one week apart (e.g., “sustained recovery”), follow-up will be censored at the last day the endpoint status was ascertained.
- Sensitivity analyses will be provided for key analyses when the outcome status is uncertain.

For **final** analyses, follow-up will be censored on the last day the outcome status was ascertained.

**Adverse events** (AEs) will be classified by system organ class according to MedDRA® (currently version 24.1 [September 2021] is used; when new versions are implemented, items are recoded). AEs will be graded according to the *DAIDS Table for Grading the Severity of Adult and Pediatric Adverse Events, Corrected Version 2.1* (July 2017) (also referred to as the *DAIDS AE Grading Table*). Cause of death will also be coded according to MedDRA®.

The number and percent of participants with grade 1-4 AEs will be summarized by day and grade, and by MedDRA® System Organ Class and grade. The percentage of participants with AEs will be compared between treatment groups according to grade cut-offs, e.g., “percent of participants with any AE”, “percent of participants with grade 2 or higher AEs”, etc., using CMH tests. The total number of events and median (IQR) of events per participant will also be summarized.

Additionally, the incidence of grade 3 and higher AEs will be summarized (number and percent of participants), and compared between treatment groups using time-to-event methods.

**Significance level, two-sided tests:** Unless noted otherwise, statistical tests and confidence intervals will be 2-sided, confidence intervals will have approximate 95% coverage probability, and test results with P-values  $\leq 0.05$  will be considered “significant”. Percentages will be reported to at least one decimal place. P-values will be given to 2 significant figures.

**Cut-date for interim reviews:** Analysis data sets will be frozen (locked) several days (or weeks) prior to the review date, to allow the unblinded statisticians time to prepare a consistent

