### 13.2 Disease Progression Risk Score

A disease progression risk score, calculated at baseline, will be used to form subgroups of participants with low or high predicted risk for subgroup analyses for safety and efficacy outcomes, and to pair participants for the win ratio analyses described in section 8.2.

The risk score for a participant is defined as the estimated *probability that the Pulmonary outcome on Day 5 is in one of the categories 5, 6 or 7* (5=non-invasive ventilation or high-flow oxygen, 6=invasive ventilation, 7=death). The probability is estimated using a logistic regression model for the corresponding binary outcome (Pulmonary categories  $\geq 5$  vs  $< 5$  on Day 5) with the following baseline predictors: age, sex, Pulmonary category at baseline, days since symptom onset, NEW score, and indicator variables for the following risk factors: asthma/COPD, diabetes, CVD, heart failure, hypertension, HIV or other immune deficiency, and renal impairment. The risk score will be derived from the pooled data for the investigational agent/placebo groups. Thus, the risk score will be specific to each investigational agent.

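### The win ratio's CI and p-value do not match its rank-pairing procedure (too narrow or too wide, depending on the risk score and arm sizes), and a stratified unmatched version has more power

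*SAP*

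**What the plan says.** SAP section 8.2 adds a win ratio to the separate analyses of recovery and death. Each arm is ordered by the baseline risk score of section 13.2, which is also used "to pair participants for the win ratio analyses described in section 8.2". Pairs are then formed by "pairing the participants in groups A (here referring to the investigational drug) and B (referring to control) with equal ranks". Step 2 compares each pair on death first and on sustained recovery second. Step 3 divides group A's wins by the number of pairs with a win or a loss, and takes the CI and p-value from a cited paper. No variance formula is printed.

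If the arms differ in size, the excess participants are deleted at random from the larger arm and the rest are paired. The instruction is then: "Repeat the random selection of observations to delete 501 times". The estimate, CI and p-value reported are those of the one data set with the median win ratio.

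Section 3 sets the general standard: "statistical tests and confidence intervals will be 2-sided, confidence intervals will have approximate 95% coverage probability". No unmatched, stratified or resampling-based win ratio is planned.

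**The concern.** A matched-pairs interval is valid if pairs are independent and the reported statistic comes from one pairing. Neither condition is safe here.

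- **Equal arms.** Ranking within each arm and pairing equal ranks does not remove a chance difference in risk between the arms. If one arm happens to be sicker, most pairs lean the same way. Pair results are then correlated, and a binomial SE leaves that out. The more prognostic the score, the larger the omission.
- **Unequal arms.** The median over 501 re-pairings averages out pairing noise, so the reported estimate varies less than a single pairing would. The reported SE is still that of a single pairing. This pushes the error the other way.

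Each participant also enters only one comparison, which discards information. Section 8.3 refers to two key endpoints in section 8.2, and this is one of them. A wrong interval could mislead in either direction on whether an agent helps when death and recovery are weighed together.

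**Working it through.** **Inputs from the documents**
- Size: "The planned sample size for each pairwise comparison is 1,000 participants (500 participants in each group" (section 1.4).
- Design: "recovery rate ratio (RRR) of 1.25 for time to sustained recovery with 90% power, using a one-sided test with a significance level of 0.025" (section 1.4).
- Events: "This requires 843 primary events (i.e., participants who achieve sustained recovery" (section 1.2, Sample size). With "planned sample size of 1,000 participants followed for 90 days will yield the planned number of 843 primary events" (section 1.4), recovery by Day 90 is 843/1,000 = 84.3%.
- Deaths before recovery: 138/1,417 = 9.7% (Table E-1, AZD7442).
- mITT totals: 1,417 (E-1) and 485 (Appendix G). Both are odd, so the arms cannot be equal and the 501-fold rule applies to both agents.

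**The plan's own figure.** Events = 4(1.960 + 1.282)²/(ln 1.25)² = 844.1, so 845. Power with 843 events is 0.8996. The stated 843 is reproduced. The SAP gives no power, variance or error rate for the win ratio.

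**Assumptions**
- SE = √[p(1−p)/(W+L)], with W wins, L losses and p = W/(W+L). This is the natural reading of a matched-pairs method, but it is not SAP text.
- Score strength, as AUC for death and Spearman correlation with outcome: none 0.50 and 0; weak 0.62 and 0.23; moderate 0.72 and 0.42; strong 0.81 and 0.61.
- Arm splits are assumed. The score is treated as known rather than fitted, and censoring is administrative at Day 90 only.

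**Type I error (two-sided 5%).** The SE ratio r is the true SE divided by the reported SE. As a check, the error implied by r is 2[1 − Φ(1.96/r)].

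| Arms | Score | r | Implied | Simulated |
|---|---|---|---|---|
| 500/500, one pairing | none | 0.997 | 4.9% | 5.0% |
| | weak | 1.017 | 5.4% | 5.4% |
| | moderate | 1.070 | 6.7% | 6.8% |
| | strong | 1.200 | 10.2% | 10.3% |
| 505/495, median of 501 | none | 0.875 | 2.5% | 2.6% |
| | weak | 0.900 | 2.9% | 3.1% |
| | moderate | 0.962 | 4.2% | 4.0% |
| | strong | 1.125 | 8.2% | 8.6% |
| 714/703, median of 501 | none | 0.874 | 2.5% | 2.8% |
| | weak | 0.899 | 2.9% | 3.2% |
| | moderate | 0.961 | 4.1% | 4.9% |

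The table rests on 10,000 null runs at 500/500, 6,000 at 505/495 (2,000 for the strong score) and 3,000 at 714/703. A strong score at 714/703 gave 8.7% in a separate set of 2,500 runs. At 248/237, about the size of MP0420, the results were 2.1% (none), 3.4% (moderate) and 7.0% (strong). At 501/499 they were 3.4%, 5.7% and 9.6%. With equal arms, null coverage of the 95% CI was about 0.95, 0.945, 0.93 and 0.89 from no score to strong. Other simulation set-ups gave equal-arm errors up to 11.2% with a strong score, and unequal-arm errors from 1.3% (none) to 10.1% (strong).

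**Comparator.** An unmatched win ratio in five risk strata with U-statistic variance had type I error of 4.7–5.7% in the largest runs, and 3.6–5.9% in smaller sets.

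**Power**

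| Setting | Matched | Unmatched, 5 strata |
|---|---|---|
| 500/500, RRR 1.25, no death effect | 0.52–0.54 | 0.65–0.68 |
| 500/500, RRR 1.25, death HR 0.8 | 0.69–0.72 | 0.82–0.86 |
| 714/703, RRR 1.25, death HR 0.8 (none to moderate) | 0.86–0.88 | 0.94–0.95 |

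Across all set-ups the loss was about 10–18 points at 500 per arm. At about 710 per arm it was 6–8 points, in runs that included the death effect. With unequal arms and an uninformative score, part of the loss is conservatism: at 714/703, after setting both tests to exactly 5%, power was 0.916 against 0.945. Stratification matters too. At 505/495 with a strong score and no death effect, the unmatched test without strata had power 0.46, against 0.62 with five strata.

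**The case against.** A reader might infer that the false-positive rate exceeds 5%, and the CI is too narrow, whenever the score is prognostic. The documents do not support that. It describes a single pairing with exactly equal arms, whereas both mITT totals in the SAP are odd. Under the 501-fold rule the test is conservative for a weak score and roughly nominal for a moderate one. Excess error then needs a strong score. The score predicts Day 5 pulmonary categories 5–7, not recovery or death through Day 90, so strength cannot be presumed. This objection stands, and it limits the claim to a mismatch whose direction varies.

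The binomial SE is a reading of a cited method. That also stands, and every error rate here depends on it.

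The win ratio supplements other analyses, has no alpha allocated to it and drives no stopping rule. Nor is it the only analysis that combines death and recovery. Section 8.1 compares median days to recovery with deaths set to 91 days, and section 8.3 scores days alive outside hospital as 0 for death. This lowers the importance of the point but does not make the interval right.

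Finally, the SAP sets no power target for the win ratio, so the lost power is inefficiency and not invalidity. That is fair, but the loss is avoidable at little cost.

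**Conclusion.** The concern holds as a mismatch between the reported SE and the procedure, not as a one-sided bias. Type I error ranges from about 1–3% (unequal arms, uninformative or weak score) to about 10–11% (equal arms, strong score), around a nominal 5%. Which end applies depends on the score's prognostic strength, which the documents do not state, and on whether the arms happen to be equal. The power loss against a stratified unmatched win ratio appeared in every scenario run. All figures assume a binomial SE over decided pairs and the simulation settings listed. The change should be made before unblinding, but the primary analysis and its conclusion do not depend on it.

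**What to change.** In section 8.2, replace rank pairing by an unmatched win ratio stratified by risk-score quintile. Compare every investigational participant with every control participant in the same quintile under the existing Step 2 hierarchy, and sum wins and losses over quintiles. Take the variance from the U-statistic (Finkelstein–Schoenfeld) or from a permutation test. Random deletion is then no longer needed, nor is random tie-breaking to form pairs.

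If rank pairing is kept, obtain the CI and p-value by re-randomization or bootstrap that repeats the whole sequence of ranking, deletion, pairing and taking the median. In either case, print the variance formula.

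The cost is a revised paragraph and a short program, with no new data. Section 1.1 already provides for SAP updates before each agent is unblinded. The small downside is that individual matching on risk becomes matching within quintiles.
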